## **12.4 Measurements of Product Compliance**

Non compliance to product allocation will be tracked by protocol deviations and summarized as described in Section 12.2 "Disposition of Subjects".

## **12.5 Extent of Exposure (Product Consumption)**

Details of the product test and product use with all products will be listed. The number and percentage of subjects using 1, 2 or 3 P3P 3 products at product test, the number of puffs and duration of product use during the fixed puffing regimen and the number of products used and the total duration of product use during the ab libitum use (calculated as the sum of the durations of each product use) will be summarized per product variant for PK population and Safety (Listing 15.3.2.1, Tables 15.2.2.1 and 15.2.2.2).

## **12.6 Planned Statistical Analyses**

### **12.6.1 Primary Analyses**

Background-corrected and uncorrected Nicotine concentrations and PK parameters will be derived as described in Section 7.1 "Pharmacokinetic Parameters".

Background-corrected and uncorrected PK parameters  $cC_{max}$ ,  $cAUC_{fix(0-4h)}$ ,  $ct_{max}$ ,  $C_{max}$ ,  $AUC_{fix(0-4h)}$  and  $t_{max}$  for fixed puffing regimen will be summarized by P3P variant.

The individual plasma nicotine concentrations over time and PK parameters will be summarized by P3P variant as detailed in section 12.1.3 "Descriptive Statistics" and will be presented by sex as described in Section 12.1.1 "Stratified Presentation" (Tables 15.2.3.1 and 15.2.3.1.1 for background-corrected concentrations, Tables 15.2.3.2 and

### **Confidentiality Statement**

15.2.3.2.1 for uncorrected concentrations, Tables 15.2.3.3 and 15.2.3.3.1 for background-corrected PK parameters, Tables 15.2.3.4 and 15.2.3.4.1 for uncorrected PK parameters).

The individual uncorrected and background-corrected plasma nicotine concentrations and actual sampling times will be listed (Listing 15.3.3.1).

The individual uncorrected and background-corrected PK parameters will be listed (Listing 15.3.3.2).

The individual plasma nicotine concentrations up to 4 hours will be plotted by P3P variant in a linear and semi-logarithmic scale (Figures 15.1.3.1 and 15.1.3.2 for background-corrected concentrations, Figures 15.1.3.3 and 15.1.3.4 for uncorrected concentrations).

The geometric mean plasma nicotine concentrations up to 4 hours will be plotted by P3P variant and their 95% CI (Figures 15.1.3.5 and 15.1.3.6 for background-corrected concentrations, Figures 15.1.3.7 and 15.1.3.8 for uncorrected concentrations).

Boxplots of  $cC_{max}$ ,  $cAUC_{fix(0-4h)}$ ,  $C_{max}$  and  $AUC_{fix(0-4h)}$  by P3P variant will be presented (Figure 15.1.3.9- 15.1.3.12).

A mixed model will be conducted on logarithmically transformed PK parameters for  $cC_{max}$ ,  $cAUC_{fix(0-4h)}$ ,  $C_{max}$  and  $AUC_{fix(0-4h)}$  with fixed terms for sequence, product variant and two dummy variables for Day 3 and Day 4 (i.e two variables taking value 1 for Day 3 and Day 4 respectively and value 0 for the other study days) and using subject nested within sequence as random effect. In this way Day 1 and Day 2 will be combined to address the multicollinearity as planned in the protocol. The SAS code to be used is shown below:

```
proc mixed data=_data_;  
  class Sequence Product_Variant Day3 Day4 Subject;  
  model logPK_Parameter = Sequence Product_Variant Day3 Day4 / ddfm=SAT s;  
  random Subject(Sequence) / sub=Subject type=CSH;  
  lsmeans Product_Variant / cl diff alpha=0.05;  
run;
```

In case of model convergence issues, this will be reported in the study report and the variance component (type=VC) covariance structure will be investigated.

Geometric least square means and ratios will be presented for the analysis of  $cC_{max}$ ,  $cAUC_{fix(0-4h)}$ ,  $C_{max}$  and  $AUC_{fix(0-4h)}$  together with 95% CI by sex and overall for the following effects of interest (Tables 15.2.3.5, 15.2.3.5.1, 15.2.3.6 and 15.2.3.6.1):

- P3P 2 vs P3P 3, to describe the effect of a decrease of nicotine powder concentration from 2 mg to 1 mg.
- P3P 2 vs P3P 4, to describe the effect of a decrease from 2.25  $\mu m$  to 1.8  $\mu m$  of the median particle size in the nicotine powder
- P3P 2 vs P3P 1, to describe the effect of flavor

A sensitivity analysis will be conducted on  $C_{max}$ ,  $cC_{max}$ , AUC and  $cAUC$  by including the study day in the model and restricting the analysis to P3P 1, 2 and 4 at study Days 2, 3 and 4 (Tables 15.2.3.5.2 and 15.2.3.6.2)

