## Protocol P3P-PK-01-CH

## Statistical Analysis Plan

Final v2.0 / 30 Apr 2018

Confidential

Page 38 of 90

we are expecting a low drop-out rate, 3 subjects will be allocated to each sequence. Therefore, 18 subjects will be randomized.

A sufficient number of eligible subjects will be enrolled and exposed to P3P 3 at Admission (Day -1) and Day 1 to ensure randomization of 18 subjects to one of six possible sequences at Day 2.

A sensitivity analysis was added in Section 12.6.1 "Primary Analyses" to evaluate the impact of including the Study Day in the analysis of specific PK parameters.

The definitions of enrolled population and randomized population were added

No shift table for ECG data will be provided.

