### **12.1.7 Significance Level for Inferential Analysis**

This study has no formal pre-specified hypotheses associated with the study objectives. Unless stated otherwise, all quoted confidence intervals are two-sided 95% confidence intervals (CI)

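### The SAP codes the random subject effect with `type=CSH`, which does not match the single subject effect in the text; fitted as coded, it makes the LS-mean confidence intervals too narrow.

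*SAP*

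**What the plan says.** Protocol 12.5.3 and SAP 12.6.1 both specify the mixed model for log-transformed PK parameters "using subject nested within sequence as random effect". Neither mentions variances that differ between subjects or gives a reason for them.

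The SAP 12.6.1 code has the fixed part "model logPK_Parameter = Sequence Product_Variant Day3 Day4 / ddfm=SAT s" and the random part "random Subject(Sequence) / sub=Subject type=CSH". Results come from "lsmeans Product_Variant / cl diff alpha=0.05", so both the LS means by variant and their differences are reported with 95% intervals.

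The same RANDOM line is in both blocks of SAP 12.6.2.2.1 (VAS craving, AUC of VAS), in 12.6.2.2.2 (adapted mCEQ) and in 12.6.2.2.3 (sensory questionnaire). SAP 12.6.2.1 carries the 12.6.1 approach over to *ad libitum* PK.

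On convergence the SAP says: "In case of model convergence issues, this will be reported in the study report and the variance component (type=VC) covariance structure will be investigated". It does not define a convergence issue.

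**The concern.** Heterogeneous compound symmetry gives each level of an effect its own variance. Here the levels are the subjects. Each subject contributes one intercept, so each variance would rest on a single realised value.

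REML can then set many of these variances to zero. The corresponding subjects receive most of the weight in their sequence mean, and the model reports the result as precise. A run that finishes without complaint keeps this structure, because the form matching the text is considered only when something visibly fails.

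The LS means and their intervals are at stake. They are planned output, and protocol 4.2 gives them a purpose: the two nicotine contents are tested to see which comes closer to the plasma levels reached after one cigarette. With no cigarette arm, that question turns on each variant's absolute level rather than on ratios between variants.

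**Working it through.** **The plan's own figure.** SAP section 8 states that "3 subjects will be allocated to each sequence", over six sequences: 6 × 3 = 18 randomized, as stated. The documents give no SD, interval width or coverage, so the SDs below are assumptions shown as a range.

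**Parameter count.** There are 18 subjects × 4 days = 72 records. The fixed effects have rank 1 + 5 (sequence) + 3 (variant) + 2 (Day 3, Day 4) = 11.

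- One variance: 1 between-subject parameter plus the residual.
- CSH on an 18-level effect: 18 variances + 1 correlation, plus the residual.
- Between-subject information after fitting sequence: 18 − 6 = 12 degrees of freedom, or 2 per sequence for 3 variances.

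The correlation enters only as a covariance between two levels in the same subject block. Each subject occupies only its own level, so this term never reaches the likelihood. What remains for subject *j* is Var(y_j) = σ_j² J + σ_w² I.

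**Effect on the weights.** Within a sequence, a subject's mean is weighted in proportion to 1/(σ_j² + σ_w²/4). A variance estimated at zero gives the largest possible weight.

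**One-variance reference.** With σ_b = 0.4 and σ_w = 0.3, a variant mean over 18 subjects has SE √((0.16 + 0.09)/18) = 0.118. The Day 3 and Day 4 terms raise this to 0.121 for P3P 2.

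**Simulation.** SAP sequences, 72 records, REML, Satterthwaite degrees of freedom, 600 datasets per row, P3P 2 LS mean. Width is CSH relative to one variance: median (5th to 95th percentile).

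| SD between/within | Relative width | Coverage, CSH | Coverage, one variance | Mean variances at zero, of 18 |
|---|---|---|---|---|
| 0.6/0.2 | 0.36 (0.25-0.51) | 49.0% | 95.5% | 7.8 |
| 0.4/0.2 | 0.50 (0.36-0.67) | 63.2% | 94.2% | 8.6 |
| 0.5/0.3 | 0.57 (0.41-0.74) | 68.0% | 93.3% | 9.0 |
| 0.4/0.4 | 0.75 (0.59-0.90) | 80.5% | 94.0% | 10.2 |
| 0.2/0.4 | 0.90 (0.79-0.98) | 88.8% | 95.0% | 12.0 |
| 0.1/0.4 | 0.95 (0.87-0.99) | 92.0% | 95.2% | 13.1 |

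Two smaller simulations at 0.4/0.3 gave:

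- 150 datasets: mean SE 0.079 against 0.121, coverage about 79%.
- 60 datasets: mean SE 0.078 against 0.120, coverage about 73%.

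The SE ratio is 0.65 in both (0.079/0.121 and 0.078/0.120). The Monte Carlo SEs of the two coverages are √(0.79 × 0.21/150) = 3.3 points and √(0.73 × 0.27/60) = 5.7 points, so the two results agree.

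**Ratios.** With complete data every subject uses every variant once, so the subject intercept cancels from each contrast. For example, P3P 2 against P3P 1 has SE σ_w√(2/18), with no σ_j in it. Only the residual estimate moves: its SD is 0.95 to 0.98 of the one-variance value. For P3P 2 against P3P 3, CSH coverage was 92.8% to 94.0% over the six rows, against 94.2% with one variance.

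**The case against.** **Software.** SAS was not run, and the figures assume that it fits one variance per subject. If it builds one column per subject, CSH reduces to a single variance and the intervals equal those under VC. This stands. The option would then be redundant, and still not what the text describes.

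**Fallback.** An uninformed correlation and many zero variances may well trigger a warning and bring in VC. This is only a partial answer: the trigger is undefined, VC is only to be investigated, and an apparently clean CSH run would be kept.

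**Reach.** The named effects of interest are the three P3P 2 comparisons, which hardly change. No hypothesis is tested, and SAP 12.1.8 says no claim will rest on individual intervals. This limits the consequence to the LS-mean intervals. A descriptive 95% interval should still cover close to 95%.

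**Stronger readings to avoid.** A reader might infer that the intervals are far too narrow whenever the model converges. The documents do not support that: the shortfall is small when within-subject SD dominates, and no SD is given.

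A reader working from subject means averaged over all four variants would also find a worse picture. At 0.4/0.3 the one-variance SE is √((0.16 + 0.09/4)/18) = 0.101, against 0.047 under CSH, with coverage of about 65%. That is the grand mean, which the SAP does not report; the product LS means also carry within-subject variance.

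**Conclusion.** Wrong as written: the code does not implement the random effect that both documents describe. If SAS fits it literally, the LS-mean intervals err on the narrow side in every setting examined. The shortfall is severe when between-subject SD clearly exceeds within-subject SD, moderate when the two are equal, and minor when within-subject SD dominates.

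The size rests on assumed SDs and on simulations outside SAS. The finding does not extend to the product ratios on complete data; missing periods would weaken that protection.

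The by-sex analyses have 8 to 10 subjects over six sequences, or 8/6 = 1.3 to 10/6 = 1.7 per sequence. Subject variances are even less estimable there. Those analyses were not simulated.

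**What to change.** Make the single-variance form the planned model. Replace the RANDOM line with `random intercept / subject=Subject(Sequence);`, without `type=CSH`, in all five code blocks: PK parameters (12.6.1, and hence *ad libitum* PK under 12.6.2.1), VAS craving and AUC of VAS (both in 12.6.2.2.1), adapted mCEQ (12.6.2.2.2) and sensory questionnaire (12.6.2.2.3). The REPEATED statement in the VAS craving model is a separate matter and is not covered by this change.

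The cost is one line of code per model, with no statistical downside. The VC fallback sentence then becomes unnecessary for the RANDOM statement.

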#### Confidentiality Statement

The analysis of  $t_{max}$  and  $ct_{max}$  will be performed by calculating the median  $t_{max}$  and  $ct_{max}$  for each P3P variant and the median difference between the P3P variants for the effect of interest mentioned above along with the Hodges-Lehmann (*Hodges and Lehmann, 1963*) 95% CI estimates (Tables 15.2.3.7 and 15.2.3.7.1 for stratified presentation).

All figures, summaries, and analysis will be produced for the PK population.

## 12.6.2 Secondary Analyses

### 12.6.2.1 Pharmacokinetics

The same approach as for the Section 12.6.1 "Primary Analyses" will be conducted for the following background-corrected and uncorrected secondary PK parameters for *ad libitum* use:  $cC_{peak}$ ,  $cC_{trough}$ ,  $cC_{average}$ ,  $cAUC_{ad lib (0-4h)}$ ,  $ct_{peak}$ ,  $C_{peak}$ ,  $C_{trough}$ ,  $C_{average}$ ,  $AUC_{ad lib (0-4h)}$  and  $t_{peak}$ .

Background-corrected and uncorrected PK parameters for *ad libitum* use will be summarized by P3P variant.

The individual plasma nicotine concentrations over time and PK parameters will be summarized by P3P variant as detailed in section 12.1.3 "Descriptive Statistics" and will be presented by sex as described in Section 12.1.1 "Stratified Presentation" (Tables 15.2.3.8 and 15.2.3.8.1 for background-corrected concentrations, Tables 15.2.3.9 and 15.2.3.9.1 for uncorrected concentrations, Tables 15.2.3.10 and 15.2.3.10.1 for background-corrected PK parameters, Tables 15.2.3.11 and 15.2.3.11.1 for uncorrected PK parameters).

The individual uncorrected and background-corrected plasma nicotine concentrations and actual sampling times will be listed (Listing 15.3.3.3).

The individual uncorrected and background-corrected PK parameters will be listed (Listing 15.3.3.4).

The individual plasma nicotine concentrations over time will be plotted up to 4 hours by P3P variant in a linear and semi-logarithmic scale (Figures 15.1.3.13 and 15.1.3.14 for background-corrected concentrations, Figures 15.1.3.15 and 15.1.3.16 for uncorrected concentrations).

The geometric mean plasma nicotine concentrations over time will be plotted up to 4 hours by P3P variant and their 95% CI (Figures 15.1.3.17 and 15.1.3.18 for background-corrected concentrations, Figures 15.1.3.19 and 15.1.3.20 for uncorrected concentrations).

Boxplots of  $cC_{peak}$ ,  $cC_{trough}$ ,  $cC_{average}$ ,  $cAUC_{ad lib (0-4h)}$ ,  $C_{peak}$ ,  $C_{trough}$ ,  $C_{average}$  and  $AUC_{ad lib (0-4h)}$  by P3P variant will be presented (Figures 15.1.3.21-28).

Geometric least square means and ratios will be presented for the analysis of  $cC_{peak}$ ,  $cC_{trough}$ ,  $cC_{average}$ ,  $cAUC_{ad lib (0-4h)}$ ,  $C_{peak}$ ,  $C_{trough}$ ,  $C_{average}$  and  $AUC_{ad lib (0-4h)}$  together with 95% confidence interval by sex and overall for the following effects of interest (Table 15.2.3.12, Table 15.2.3.12.1, Table 15.2.3.13 and Table 15.2.3.13.1):

- P3P 2 vs P3P 3, to describe the effect of a decrease of nicotine powder concentration from 2 mg to 1 mg.

#### Confidentiality Statement

- P3P 2 vs P3P 4, to describe the effect of a decrease from 2.25  $\mu\text{m}$  to 1.8  $\mu\text{m}$  of the median particle size in the nicotine powder
- P3P 2 vs P3P 1, to describe the effect of flavor

A sensitivity analysis will be conducted on  $\text{cC}_{\text{peak}}$ ,  $\text{cC}_{\text{trough}}$ ,  $\text{cC}_{\text{average}}$ ,  $\text{cAUC}_{\text{ad lib (0-4h)}}$ ,  $\text{C}_{\text{peak}}$ ,  $\text{C}_{\text{trough}}$ ,  $\text{C}_{\text{average}}$  and  $\text{AUC}_{\text{ad lib (0-4h)}}$  by including the study day in the model and restricting the analysis to P3P 1, 2 and 4 at study Days 2, 3 and 4 (Tables 15.2.3.12.2 and 15.2.3.13.2).

The analysis of  $t_{\text{peak}}$  and  $ct_{\text{peak}}$  will be performed by calculating the median  $t_{\text{peak}}$  and  $ct_{\text{peak}}$  for each P3P variant and the median difference between the P3P variants for the effect of interest mentioned above along with the Hodges-Lehmann (*Hodges and Lehmann, 1963*) 95% CI estimates (Table 15.2.3.14 and Table 15.2.3.14.1 for stratified presentation).

## 12.6.2.2 Questionnaires

### 12.6.2.2.1 Visual Analogue Scale for Craving

The values of VAS for Craving and changes from baseline for fixed puffing regimen will be summarized by P3P variant and time point (Table 15.2.4.1) and listed (Listing 15.3.4.1). Individual profiles and profiles of the raw means will be produced by P3P variant and time point (Figures 15.1.4.1, 15.1.4.2).

A mixed model will be conducted for the values of VAS for Craving for fixed puffing regimen with fixed terms for sequence, product variant, two dummy variables for Day 3 and Day 4 (i.e two variables taking value 1 for Day 3 and Day 4 respectively and value 0 for the other study days), baseline value prior to product use, the time point and the interaction of product variant and time point and using subject nested within sequence as a random effect including the assessment timepoints as repeated measurements. In this way Day 1 and Day 2 will be combined to address the multicollinearity as planned in the protocol. The SAS code to be used is shown below:

```
proc mixed data=_data_;  
  class Sequence Product_Variant Day3 Day4 Time_Point Subject;  
  model VAS = Sequence Product_Variant Day3 Day4 VAS_Baseline  
  Product_Variant*Time_Point / ddifm=SAT s;  
  repeated Time_Point / subject=Subject type=CSH;  
  random Subject(Sequence) / sub=Subject type=CSH;  
  lsmeans Product_Variant / cl diff alpha=0.05;  
  lsmeans Product_Variant*Time_Point / slice=Time_Point alpha=0.05 diff cl;  
run;
```

In case of model convergence issues, this will be reported in the study report and the variance component (type=VC) covariance structure will be investigated.

Least square means and differences will be presented for the analysis of the values of VAS for Craving together with 95% confidence interval for the following effects of interest (Table 15.2.4.2):

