## 7.3 Questionnaires

### 7.3.1 VAS Craving Assessments

A VAS-craving assessment will be used to assess the level of craving of the subject based on their response to the question, "How strong is your craving for cigarettes?" on a scale of 0 (no craving) to 10 (strong craving).

The VAS craving will be completed by the subject at Days 1 to 4. For the fixed puffing regimen the first assessment will be done 15 minutes  $\pm$  5 minutes prior to  $T_0$  fix, all other assessments will be done after  $T_0$  fix, at 4 minutes  $\pm$  2 minutes, at 10 minutes  $\pm$  2 minutes, at 15 minutes  $\pm$  2 minutes, 30 minutes  $\pm$  5 minutes, 1 hour, 2 hours, 4 hours  $\pm$  10 minutes each.

For the *ad libitum* use period the first assessment will be done 15 minutes  $\pm$  5 minutes prior to  $T_0$  ad lib, all other assessments will be done after  $T_0$  ad lib, at 10 minutes  $\pm$  2 minutes, at 20 minutes  $\pm$  2 minutes, 30 minutes  $\pm$  5 minutes, 40 minutes  $\pm$  5 minutes, 1 hour, 2 hours, 4 hours  $\pm$  10 minutes each.

For the VAS craving score  $AUC_{VAS}$  will be derived for each puffing regimen ( $AUC_{VAS\ fix\ (0-4h)}$  and  $AUC_{VAS\ ad\ lib\ (0-4h)}$ ) using trapezoidal rule.

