### **12.1.8 Multiple Comparisons/Multiplicity**

No formal adjustment of the test-wise alpha level for multiple testing is necessary, as this study is descriptive in nature and no claim will be made based on the outcome of the individual CI values.

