#### Confidentiality Statement

Data and information contained in this document are considered to constitute trade secrets and confidential commercial information, and the legal protections provided to such trade secrets and confidential information are hereby claimed under the provisions of applicable law. No part of this document may be publicly disclosed without the written consent of Philip Morris Products S.A.

- P3P 2 vs P3P 3, to describe the effect of an increase of nicotine powder concentration from 2.5% to 5%
- P3P 2 vs P3P 4, to describe the effect of a decrease from 2.25  $\mu\text{m}$  to 1.8  $\mu\text{m}$  of the median particle size in the nicotine powder
- P3P 2 vs P3P 1, to describe the effect of flavor

The values of  $\text{AUC}_{\text{VAS fix (0-4h)}}$  will be summarized by P3P variant (Table 15.2.4.3) and listed (Listing 15.3.4.2). Boxplot of  $\text{AUC}_{\text{VAS fix (0-4h)}}$  by P3P variant will be presented (Figure 15.1.4.3).

A mixed model will be conducted for the values of  $\text{AUC}_{\text{VAS fix (0-4h)}}$  for fixed puffing regimen with fixed terms for sequence, product variant and two dummy variables for Day 3 and Day 4 (i.e two variables taking value 1 for Day 3 and Day 4 respectively and value 0 for the other study days) and using subject nested within sequence as random effect. In this way Day 1 and Day 2 will be combined to address the multicollinearity as planned in the protocol. The SAS code to be used is shown below:

```
proc mixed data=_data_;  
  class Sequence Product_Variant Day3 Day4 Subject;  
  model AUCVAS fix (0-4h) = Sequence Product_Variant Day3 Day4 / ddfm=SAT s;  
  random Subject(Sequence) / sub=Subject type=CSH;  
  lsmeans Product_Variant / cl diff alpha=0.05;  
run;
```

In case of model convergence issues, this will be reported in the study report and the variance component (type=VC) covariance structure will be investigated.

Least square means and differences will be presented for the analysis of  $\text{AUC}_{\text{VAS fix (0-4h)}}$  together with 95% confidence interval for the following effects of interest (Table 15.2.4.4):

- P3P 2 vs P3P 3, to describe the effect of an increase of nicotine powder concentration from 2.5% to 5%
- P3P 2 vs P3P 4, to describe the effect of a decrease from 2.25  $\mu\text{m}$  to 1.8  $\mu\text{m}$  of the median particle size in the nicotine powder
- P3P 2 vs P3P 1, to describe the effect of flavor

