The values of VAS for Craving and changes from baseline for *ad libitum* use will be summarized by P3P variant and time point (Table 15.2.4.5) and listed (Listing 15.3.4.3). Individual profiles and profiles of the raw means will be produced by P3P variant and time point (Figures 15.1.4.4 and 15.1.4.5).

The same mixed model as for fixed puffing regimen will be conducted for the values of VAS for Craving for *ad libitum* use. Least square means and differences will be presented for the analysis of the values of VAS for Craving for *ad libitum* use together with 95% confidence interval for the same effects of interest of VAS for Craving for fixed puffing regimen (Table 15.2.4.6).

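### The VAS craving model blocks repeated time points by subject instead of subject-by-day: it cannot be fitted as coded, and the type=VC fallback can make the overall product confidence intervals too narrow

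*SAP*

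**What the plan says.** SAP 7.3.1 states: "The VAS craving will be completed by the subject at Days 1 to 4". For each regimen it lists one pre-use reading and seven post-use readings per day. Each day uses one product variant (SAP Appendix 16.1, footnote j), so subject-by-day and subject-by-product are the same unit.

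SAP 12.6.2.2.1 puts the four days into one PROC MIXED call. The text describes "using subject nested within sequence as a random effect including the assessment timepoints as repeated measurements". The code has "repeated Time_Point / subject=Subject type=CSH" and one random intercept per subject, "random Subject(Sequence) / sub=Subject type=CSH". Neither text nor code has a subject-by-day term. Protocol 12.6.2.2, under VAS Craving Assessments, also names only the subject as random effect.

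Overall product differences come from "lsmeans Product_Variant / cl diff alpha=0.05"; a second LSMEANS line gives differences at each time point. If convergence fails, this is to be reported and "the variance component (type=VC) covariance structure will be investigated". For ad libitum use, "The same mixed model as for fixed puffing regimen will be conducted".

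**The concern.** The SUBJECT= option on REPEATED defines the block within which each level of the repeated effect should occur once. Here the block is the person, who passes through the same seven nominal times on four days. The model therefore treats the 4-minute score on Day 1 and the 4-minute score on Day 4 as the same measurement.

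The fallback sentence does not say whether VC replaces CSH on REPEATED, on RANDOM or on both. The same sentence follows the AUC code in that section, which has only a RANDOM statement, so the text does not settle it.

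At stake are the 95% intervals for the overall product differences in Tables 15.2.4.2 (fixed puffing) and 15.2.4.6 (ad libitum). The study tests no hypotheses, so these intervals are its inferential output on craving scores.

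**Working it through.** **Inputs.** 18 randomised subjects (6 sequences x 3, SAP section 8); 4 days each; 7 post-use scores per day and regimen (SAP 7.3.1). Records per subject: 4 x 7 = 28. Records in total: 18 x 28 = 504. The correlation r between same-day scores, given the subject, is in neither document and is assumed below.

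**Can the coded model be fitted?** Let C be the 7 x 7 CSH matrix over time points, and let J4 and J7 be all-ones matrices.

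- As coded, R = J4 ⊗ C. Adding the subject intercept gives V = J4 ⊗ (C + σ²J7). J4 has rank 1, so R and V have rank at most 7 out of 28. A numerical check at CSH correlations 0, 0.3, 0.6 and 0.9 gave rank 7 for both each time. The determinant is zero, so the likelihood is undefined.
- With subject-by-day blocks, V = I4 ⊗ C + σ²J28. The rank was 28 each time.
- VC on RANDOM alone changes nothing: with one intercept per subject, CSH and VC are the same single variance, and R keeps rank 7.
- VC on REPEATED gives rank 28 and can be fitted.

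**What VC on REPEATED does to the overall contrast.** Product is constant within a day, so the error of an overall product difference comes from day means. Set the within-subject variance to 1 and assume constant same-day correlation r. A day mean then has variance (1 + 6r)/7. VC uses s²/7, with s² pooled over all records.

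With subjects as fixed blocks, the day-mean model has 18 subject + 3 product + 2 day + 1 baseline = 24 parameters, leaving 72 - 24 = 48 df. The remainder within days has 504 - 72 - 24 = 408 df (24 = 4 products x 6 time contrasts). Hence

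E(s²) = [48(1 + 6r) + 408(1 - r)] / 456

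SE ratio (correct / VC) = √[(1 + 6r) / E(s²)]; approximate coverage = 2Φ(1.965 / ratio) - 1.

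| r | E(s²) | SE ratio | coverage |
|---|---|---|---|
| 0 | 1.000 | 1.00 | 0.95 |
| 0.1 | 0.974 | 1.28 | 0.87 |
| 0.3 | 0.921 | 1.74 | 0.74 |
| 0.5 | 0.868 | 2.15 | 0.64 |

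**Simulation of overall-contrast coverage under VC on REPEATED**, using the SAP's design and three contrasts:

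| Setting | r = 0 | 0.1 | 0.3 | 0.5 |
|---|---|---|---|---|
| Baseline in model, r defined after baseline adjustment (4,000 trials, subjects as fixed blocks) | 0.94-0.95 | 0.86-0.87 | 0.73-0.75 | 0.63-0.65 |
| Baseline in model, r defined before adjustment, baseline carrying the same day effect (1,000 trials, REML) | 0.95 | 0.87 | 0.78 | 0.72 |
| No baseline (1,000 trials, REML) | 0.94 | 0.88 | 0.75 | 0.64 |
| No baseline, correlation decaying at first order, r between adjacent readings (4,000 trials) | - | 0.93 | 0.86 | 0.78 |

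In the REML runs, models with subject and subject-by-day intercepts (48 df assumed) covered 0.946-0.960 throughout. Single-time-point coverage under VC was 0.93-0.95 with baseline and 0.92-0.95 without.

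**The case against.** The other side does not dispute the blocking error. It argues that the consequences are small and visible.

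- **The failure would not be silent.** Section 12.6.2.2.1 requires convergence problems to be reported, section 13.2 allows dry-run outputs before database lock, and section 3 allows changes described in the CSR. This stands, but the covariance structure would then be chosen with study data in hand.
- **The ambiguity is limited.** Because VC on RANDOM alone changes nothing, only VC on REPEATED (or on both) yields a fit. This also stands. The main fault of the fallback is the missing subject-by-day term.
- **Little rests on it.** The endpoint is secondary, and SAP 12.1.8 says that "no claim will be made based on the outcome of the individual CI values". The AUC of the VAS has one value per subject-day and does not share the fault, although it is time-weighted and so a different quantity from the mean of seven readings. This limits the severity, but the SAP still commits to presenting the intervals as 95% intervals.
- **The size depends on the assumed pattern.** Decaying correlation roughly halves the loss of coverage, and the result with baseline depends on how r is defined. This stands, so a range is the right way to quote it. The direction does not change.

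**Conclusion.** The concern holds. That the coded model cannot be fitted is a matter of algebra and rests on no assumption about the data; it was shown from the covariance matrix, not from a SAS run. The narrowing under VC on REPEATED requires positive same-day correlation after the subject and baseline terms. Across the settings tried, overall coverage runs from 0.86 to 0.93 at r = 0.1, 0.73 to 0.86 at r = 0.3 and 0.63 to 0.78 at r = 0.5. Both use regimens are affected. The point should be corrected before the analysis is run, but it touches no primary endpoint.

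**What to change.** Replace the REPEATED line with `repeated Time_Point / subject=Subject*Product_Variant type=CSH;`, so that each subject-day is one block, and make the RANDOM line a plain subject intercept. Replace the VC sentence with a named fallback: a random subject-by-day intercept (or CS within subject-by-day) in addition to the subject intercept. State which statement changes. Apply the same text to ad libitum use.

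The cost is a line or two of code and one sentence. The number of R parameters stays at eight (seven variances, one correlation). Compared with VC on REPEATED, standard errors of overall product differences grow by factors of 1.26, 1.60 and 1.82 at r = 0.1, 0.3 and 0.5 (REML with baseline); with r defined after baseline adjustment, intervals widen 1.30, 1.78 and 2.18 times. Single-time-point standard errors grow by at most about 6% with baseline. These figures, and the restored coverage, come from models with subject-by-day as the error unit; CSH within subject-by-day with Satterthwaite df was not itself simulated.

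While editing, check the df option: it reads `ddifm` in this block and `ddfm` in the others, which may only be an artefact of text extraction.
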